Patients will attend the CPU in fasted state with their BronkoTest[©] diary card on the morning of Day -1 and stay until Day 3. Eligibility will be re-confirmed and safety assessments performed (vital signs, ECG, lung function, haematology, clinical chemistry and urinalysis, urine drug screen including alcohol). Twenty-four hour ambulatory cardiac monitoring (telemetry) will be started on Day -1 and monitoring continued for 24 hours post first dose. All urine produced over the 24 hours before the first dose will be collected for assessment of baseline desmosine levels and for the pre-dose urine PK. [For all timed urine collections, the patients should empty the bladder within 10 minutes of Time 0, discard that urine and then collect all the urine from then onwards. At Time (0 + t hours) they should then empty the bladder and add that to the collection.] On the morning of Day -1, the patients will provide an induced sputum sample; weight of the sample will be recorded, and the sample processed for neutrophils and AZD9668 levels. Blood will also be collected for baseline assessment of hsCRP and serum amyloid A.

Patients will fast from midnight on Day 1 until 2 hours after the first dose (water will be allowed for thirst up until 1 hour before dosing).

On Day 1, pre-dose patients will be asked to provide a spontaneous sputum sample for quantitative bacteriology. They will be randomised to receive either AZD9668 or placebo: A single dose will be administered in the morning of Day 1. All urine produced over the 24 hours after the first dose will be collected for measurement of AZD9668 concentrations. Urine will be collected for time periods 0-4 hours, 4-12 hours and 12-24 hours. Aliquots from each of these collections will be taken for urine PK, and an aliquot from the pooled sample will be taken for urine desmosine. Serial blood samples will be collected for PK analysis at pre-dose and at 0.25, 0.5, 1, 2, 3, 4, 5, 6, 8, 12, and 24 hours post dose (NB. PK samples taken at 24 h will be taken pre-dose). Vital signs and ECG will be done at approximately 1 hour after the first dose.

On Days 2 - 13 the patients will receive 2 daily doses of AZD9668. The first dose of each day will be taken at approximately the same time $(\pm 1h)$ as the first dose administered on Day 1 and the 2nd daily dose will be approximately 12 hours later $(\pm 1 \text{ hour})$.

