Further safety assessments (vital signs, ECG, lung function, haematology, clinical chemistry and urinalysis) will be done before the morning dose on Day 2. Patients will be discharged on the morning of Day 3 (after having taken the 4th dose of the study drug). Prior to discharge,

patients will be re-issued with their BronkoTest[©] diary card and sufficient tablets to allow daily self-dosing until their next visit. Vital signs will be measured and an ECG recorded before discharge. The pharmacogenetic sample can be taken at any convenient time point after the first dose.

The BronkoTest[®] diary card will be filled in for all days whilst the subject is in the CPU and at home.

Visit 3: Treatment period (Day 7 ±1 day): Patients will attend the CPU on the morning of Day 7 (±1 day) in fasted state, having fasted from midnight (water will be allowed for thirst up until 1 hour before dosing) and having withheld taking their morning dose of study medication for that day. Patients will bring with them their BronkoTest[®] diary card and any remaining study medication. Before administration of the morning dose, safety assessments (vital signs, ECG, lung function, haematology, clinical chemistry, urinalysis and urine drug screen) will be performed. Blood samples will be collected pre-dose for PK and for assessment of hsCRP and serum amyloid A. Patients will then take their morning dose of study medication in the CPU. Patients will be discharged from the CPU with their BronkoTest[®] diary card and sufficient tablets to allow daily self-dosing until their next visit.

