	Screening visit	Study Visit (start) 2				Study visit	Study visit (end) 4		Follow- up 5
Study Visit	1					3			
Study Day	-21 to -8	-1	1	2	3	7 (±1)	14(±1)	15	21 (±3)
Residential stay ^a		~	~	~	~		~	~	
Informed consent	√								
Incl./Excl criteria	✓	✓							
Demographics	✓								
Med/surgical history	✓								
Drug screen including alcohol	✓	✓				✓	✓		
Virology	✓	1					1	1	
Pregnancy test /FSH (if appropriate)	~								
Concomitant medication	~	~	✓	~	✓	~	~	✓	~
Adverse event questioning		~	~	~	✓	~	✓	✓	✓
Randomisation			✓						
Dispense study drug					✓	✓			
Physical examination	✓								✓
Vital signs ^b	✓	✓	✓	✓	✓	✓	✓		✓
12-lead ECG ^b	✓	✓	✓	✓	✓	✓	✓		✓
Telemetry		✓	✓						
Safety blood/urinalysis ^c	✓	✓		✓		✓	✓		✓
Lung function ^c	✓	✓		✓		✓	✓		✓
Induced sputum ^d		✓					✓		
Quantitative sputum bacteriology ^e			~					~	
24-h urine collection for desmosine ^f		~					~		
Urine PK ^g		✓	✓				✓		
Plasma - full PK profile ^h			✓				✓		
Plasma– single PK sample ⁱ						✓			
Serum – hsCRP, amyloid-A		✓				~	✓		✓
Plasma for multiplex analysis of cytokines (including but not limited to TNF-α, IL-8)		~					~		✓

Table 1Study plan

	Screening visit (start)			Study visit	Study visit (end)		Follow- up		
Study Visit	1	2				3	4		5
Study Day	-21 to -8	-1	1	2	3	7 (±1)	14(±1)	15	21 (±3)
BronkoTest [©] diary card ^j	✓	~	~	~	~	~	✓	✓	~
Return study drug						~	~		
Non-residential visit	~					~			✓
Genetic blood sample ^k			~						

^a Patients to be resident in the CPU from the morning of Day -1 to the morning of Day 3, and from the morning of Day 14 to the morning of Day 15.

^b Vital signs & ECG to be taken at Screening visit, Day -1, Day 1 (1h after 1st morning dose), Days 2, 3 (prior to discharge), 7 and 14 (before morning dose), and at follow-up. An additional ECG will be recorded 1 hour post-dose in Day 14..

- ^c Safety blood, urinalysis & lung function (SVC, FEV₁, FVC, IC) to be done at Screening visit, Day –1, before morning dose on Days 2, 7 & 14, and at follow-up.
- ^d Induced sputum (for sputum weight, neutrophils, & AZD9668) to be done at visit 2 (Day -1)and 1-2 hours after the last dose on Day 14.
- ^e Quantitative sputum bacteriology to be done on a spontaneous sample (pre-dose on Day1), preferably that produced first thing in the morning.

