A population PK model of the PK data from the SAD and MAD study has been developed and was used to estimate the mean population PK parameters of AZD9668 with the associated variability and to assess the affect of consumption of a high fat breakfast on the PK of AZD9668. A dose of 60 mg twice a day has been selected as the dose for the current study. This dose has been chosen as a dose that is predicted to achieve trough steady state therapeutic plasma concentrations of 19 nM (predicted from an in vivo mouse acute lung injury model) in all patients, whilst ensuring that the predicted geometric mean Cmax,ss and AUC(0-24h),ss are below the HELC limits. The estimated margins to the HELC limits in the fasted state are 2.6 and 1.4 for C_{max,ss} and AUC_{(0-24h),ss}, respectively, and this will be the dose that will be used in the subsequent proof-of-principle studies with AZD9668. If a dose of 60 mg b.i.d is not tolerated by an individual patient then his/her dose may be halved to 30 mg b.i.d for the remainder of the study, at the investigator's discretion. The population PK model predicts that this will still achieve trough steady state plasma concentrations above 19 nM in all the patients. Since the objective of the study is to investigate tolerability, the higher dose (i.e. 60 mg b.i.d) has been chosen as the study dose rather than the minimum dose that is predicted to achieve therapeutic exposures. AZD9668 will only be dosed once a day on Days 1 and 14 to enable measurement of single dose and steady state pharmacokinetics respectively.

From the population PK modelling it was identified that the bioavailability of AZD9668 was approximately 90% of that when it was administered in the fasted state. This did not however have any impact upon the dose selection. For the subsequent studies therefore, it is not necessary for the patients to restrict food around administration of their doses.

Patients will receive their morning dose in a fasted state on Days 1, 7 and 14, i.e. on days when they are having ECG measurements. This ensures that the ECG measurements can be taken when C_{max} is maximised.

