3.4.2 Doses and treatment regimens

In the current study the daily dose will be 120 mg (i.e. 60 mg b.i.d), except for days 1 and 14 when patients will receive only the morning dose to allow assessment of PK. This dose has been chosen as a dose that is predicted to achieve trough steady state therapeutic plasma concentrations of 19 nM (predicted from an in vivo mouse acute lung injury model) in all patients, whilst ensuring that the predicted geometric mean $C_{max,ss}$ and $AUC_{(0-24)ss}$ are below the HELC limits. The estimated margins to the HELC limits are 2.6 and 1.4 for $C_{max,ss}$ and $AUC_{(0-24)ss}$, respectively, in the fasted state. If a dose of 60 mg b.i.d is not tolerated by an individual patient then his/her dose may be halved to 30 mg b.i.d for the remainder of the study, at the investigator's discretion. The population PK model predicts that this will still achieve trough steady state plasma concentrations above 19 nM in all patients.

For morning doses administered on Days 1, 7 and 14, patients will be fasted from midnight the night before dosing except water for thirst. The patients may consume water up to 1 hour before dosing. The dose will be administered with 240 mL of water, and the patients must drink all the water. The patients must not consume any further fluids or food for a minimum of 2 hours post dose. At this time the patients will be allowed a light breakfast. Fasting the patients prior to receiving their morning dose on days when they are having ECG measurements ensures that the ECG measurements can be taken when C_{max} is maximised. There is no requirement to restrict food consumption before or immediately after administration of the remaining doses. These doses can be administered with approximately 100 mL water.

The morning and evening doses will be filled individually in high-density polyethylene (HDPE) bottles with a child resistant cap according to the random scheme. All bottles for morning and evening dose for 14 days will be packed in a white box for each patient.

At Visit 2, the required number of bottles needed for the morning and evening dose until Visit 3 will be handed over to the patient after the 4th dose has been taken in the CPU.

At Visit 3, the required number of bottles until Visit 4 will be handed over to the patient after the morning dose has been administered.

At Visit 4, the patient will be administered the morning dose in the CPU by the staff.

[figure not shown]

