- Evidence of haemolysis as evidenced by the following:
 - Reticulocyte count of over 5%, and

At least two of the following:

- a drop in haemoglobin below 10.5 g/dl
- decrease of 25% in haptoglobin. (The value post-dose to be compared with the average of two pre-dose values. The value should also be 15% below LLN).
- increase of 25% in unconjugated bilirubin or lactate dehydrogenase (LDH).
 (The value post-dose to be compared with the average of two pre-dose values. The value should also be 15% above ULN)
- A platelet count of below $80 \ge 10^9$ /L confirmed by a repeat test (in the absence of obvious platelet clumping in a peripheral blood film).
- A QTcF >500 ms on active treatment (QT interval corrected for heart rate by Fridericia method) or a QTcF prolongation >60 ms on average compared to baseline, confirmed by a repeat ECG in 30 minutes.

Section of protocol affected:

3.3.5, Discontinuation of patients from treatment or assessment3.3.5.1, Criteria for discontinuation, Stopping criteria for the whole study, page 30

Previous text:

Stopping criteria for the whole study

- Two or more patients on active treatment are discontinued because of either an ALT/AST level ≥3 x ULN or any pattern of LFT abnormalities giving cause for concern
- Two or more patients on active treatment are discontinued because of evidence of haemolysis
- Two or more patients on active treatment are discontinued because of a platelet count of below $80 \times 10^9/L$

Revised text:

Stopping criteria for the whole study

- Two or more patients on active treatment are discontinued because of either an ALT/AST level ≥3 x ULN or any pattern of LFT abnormalities giving cause for concern
- Two or more patients on active treatment are discontinued because of evidence of haemolysis
- Two or more patients on active treatment are discontinued because of a platelet count of below $80 \ge 10^9/L$
- A QTcF >500 ms on active treatment (QT interval corrected for heart rate by Fridericia method) or a QTcF prolongation >60 ms on average compared to baseline, confirmed by a repeat ECG in 30 minutes in 2 or more subjects on active treatment

Section of protocol affected:

Section 10, References, page 58

Added reference:

GOLD 2007

Global Initiative for Chronic Obstructive Lung Disease. Global Strategy for the Diagnosis, Management, and Prevention of Chronic Obstructive Pulmonary Disease. Updated 2007. http://www.goldcopd.org

Reason for Amendment:

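### The Day 7 ECG is justified as a reading at maximal Cmax but is scheduled before the dose, so the only ECG timed to the steady-state peak follows the last dose

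*Protocol*

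**What the plan says.** Section 3.2.1 links the fasted morning doses to the ECGs: "Patients will receive their morning dose in a fasted state on Days 1, 7 and 14, i.e. on days when they are having ECG measurements". It then gives the purpose: "This ensures that the ECG measurements can be taken when C_{max} is maximised". Section 3.4.2 repeats the argument for the same three days, saying that fasting "ensures that the ECG measurements can be taken when C_{max} is maximised".

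The schedule in Section 3.1 is different for Day 7. The Visit 3 text reads: "Before administration of the morning dose, safety assessments (vital signs, ECG, lung function, haematology, clinical chemistry, urinalysis and urine drug screen) will be performed". Table 1 footnote b agrees, listing the vital signs and ECG times as "Days 2, 3 (prior to discharge), 7 and 14 (before morning dose), and at follow-up". The footnote adds one post-dose ECG, on Day 14 only. For Day 1 the text is: "Vital signs and ECG will be done at approximately 1 hour after the first dose".

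Amendment 01 adds a QTcF criterion to Section 3.3.5.1 for stopping an individual patient, beginning "A QTcF >500 ms on active treatment (QT interval corrected for heart rate by Fridericia method", with an alternative limb for a prolongation of more than 60 ms from baseline. It adds a matching whole-study criterion when 2 or more subjects on active treatment meet it. The sections that the amendment lists as changed do not include ECG timing.

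**The concern.** An ECG recorded before the morning dose cannot be a reading at Cmax, so on Day 7 the schedule defeats the purpose stated for it. Section 3.1 and Table 1 agree with each other, so this is not a slip in one place. Analysis rules in an SAP could not cure it, because the reading would not have been taken.

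ECG and vital signs are primary tolerability variables. Section 3.2.2 gives a tendency to QT prolongation in dog telemetry studies as the reason for the QT exclusion, and Amendment 01 goes further with QTcF stopping criteria. At stake is whether those criteria see a planned reading at the highest repeated-dose exposure while the patient is still being dosed.

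**Working it through.** The protocol gives no figure to reproduce here. The check sets the passages side by side and adds a supporting calculation.

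**1. On-treatment readings (Section 3.1 and Table 1)**

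| Day | 12-lead ECG | Vital signs |
|---|---|---|
| 1 | about 1 h after dose 1 | with the ECG |
| 2 | before morning dose | before morning dose |
| 3 | before discharge; no set time after dose 4 | before discharge |
| 7 | before morning dose | before morning dose |
| 14 | before morning dose | before morning dose |
| 14 | 1 h after the final dose | none |

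Telemetry ends 24 h after the first dose (Section 4.7.3.1).

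**2. Dose count.** Day 1 has 1 dose, Days 2–13 have 12 × 2 = 24, and Day 14 has 1, giving 26. On the nominal schedule the Day 7 morning dose is number 1 + (5 × 2) + 1 = 12, which leaves 26 − 12 = 14 doses after it.

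**3. Inputs for the exposure check (Section 3.2.1).** Median tmax was 1 h after both single and multiple dosing in the multiple-dose part. Geometric mean steady-state half-lives were 9.04, 10.24 and 8.73 h. The single-dose range was 5.04 to 14.99 h.

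**4. Model (an assumption).** One compartment, instantaneous input, superposition. Let r(h) = 2^(−h/t½).
- Trough over peak at 12-hourly dosing: r(12).
- Day 1 peak over steady-state peak: 1 − r(12).
- Day 3 peak (dose 4, earlier doses at 0, 24 and 36 h) over steady-state peak: [1 + r(12) + r(24) + r(48)] × [1 − r(12)].

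| t½ (h) | Trough/peak | Day 1 peak/steady state | Day 3 peak/steady state |
|---|---|---|---|
| 8.73 | 0.386 | 0.614 | 0.956 |
| 9.04 | 0.398 | 0.602 | 0.952 |
| 10.24 | 0.444 | 0.556 | 0.934 |
| 5.04 (low end, single dose) | 0.192 | 0.808 | 0.994 |
| 14.99 (high end, single dose) | 0.574 | 0.426 | 0.857 |

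The Day 7 peak is 0.998 or more of steady state across the whole range. A steady-state peak therefore occurs on Day 7, but no ECG is scheduled at it. The Day 1 reading is at peak, but of a single dose: about 56–61% of the steady-state peak for the steady-state half-lives.

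**5. What the Day 7 fast is for.** Sections 3.3.4 and 3.4.2 keep the patient fasted until 2 h after the dose. Section 3.3.4 ties fasting to PK sampling days, but the Day 7 PK sample is also taken before the dose. Fasting glucose (Section 4.7.2.1) could explain the fast before the dose. No scheduled Day 7 assessment uses the 2 h after it.

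**The case against.** **Day 3.** A reader might infer that no ECG or vital signs fall near the steady-state peak before the last dose. The documents do not support that. Patients leave on Day 3 after dose 4, with vital signs and an ECG before discharge, and on the model above the dose 4 peak is 93–96% of steady state. The reading may fall after the dose. It has no set time relative to it, however, and food is unrestricted that day. Section 3.2.1 reports that a high-fat meal moved median tmax to 3–4 h and lowered Cmax by 22–31%. Day 3 may by chance give a near-peak reading; it does not plan one.

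**Stopping criteria.** A reader might also infer that the QTcF criteria cannot act on a peak effect during repeated dosing. That is too strong. Patients are randomised sequentially (Section 3.5), so Day 14 readings in earlier patients can count toward the whole-study criterion while later patients are dosing. Day 3 and Day 7 readings can trigger the individual criterion if they exceed it. The gap is narrower: no reading timed to the steady-state peak can do so for the same patient before the last dose.

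**Prior risk.** Section 3.2.2 reports no QT prolongation in volunteers at any dose and, headache apart, no reason to link the other events to the drug. The estimated margin to the Cmax limit is 2.6. This lowers the urgency but does not reconcile the passages.

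**Deleting Day 7 from the rationale.** This would remove the contradiction in wording. It would leave the primary tolerability assessment without a timed steady-state-peak ECG until the final dose.

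**Conclusion.** The contradiction stands on the text alone: Sections 3.2.1 and 3.4.2 claim a maximal-Cmax purpose for Day 7 that Section 3.1 and Table 1 cannot meet. The Day 7 ECG and vital signs are trough readings. ECGs timed to tmax follow only doses 1 and 26, and no vital signs are scheduled at a steady-state peak. The consequence for the QTcF discontinuation criterion is confined to the individual patient.

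The percentages rest on the assumed one-compartment bolus model with the protocol's half-lives. They show that a trough reading differs materially from a peak reading and are not predictions. A model with a distribution phase would give other fractions, but the documents report no parameters from which to calculate them. The point merits correction because it touches a primary variable and is cheap to repair. It is not evidence of a safety signal.

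**What to change.** Reconcile Section 3.1 (Visits 3 and 4), Table 1 footnote b, Section 3.2.1 and Section 3.4.2, so that the stated purpose of the Day 7 fast and the time of the Day 7 ECG agree.

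If the sponsor keeps the stated purpose, it would be met by two changes:
- Record an ECG and vital signs on Day 7 at the 1-h post-dose point already used on Day 1, preferably in addition to the pre-dose reading.
- Take vital signs with the Day 14 1-h ECG.

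On the nominal schedule the Day 7 addition would give a timed steady-state-peak reading with 14 doses still to come. If the sponsor does not keep that purpose for Day 7, the rationale should drop Day 7 and say plainly that the steady-state-peak ECG is obtained only after the final dose.

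The cost is an edit to one footnote and the visit text, and about one more hour in the unit at Visit 3, inside the 2-h post-dose fast already required. If the Day 7 ECG is moved rather than added, the Day 7 trough reading and the check before that day's dose are lost; the Day 14 pre-dose ECG would still give a steady-state trough value.

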3.2.2 Risk/benefit and ethical assessment

The patients will have no individual benefit from participation in the study. The early development studies are to enable further investigations to evaluate AZD9668 as a treatment of COPD.

In the FTiM single and multiple dose-escalation study of AZD9668, the AEs that were reported included headache, nausea and vomiting. Some ECG abnormalities were also noted during 24-hour ambulatory monitoring, which included nocturnal bradycardia, a short run of premature atrial contractions and a non-sustained broad-complex tachycardia. Also one subject experienced syncope associated with a bradycardia. With the exception of headaches, which occurred consistently at high doses, there was no reason to suspect that any of the other AEs could be related to AZD9668, as no consistent pattern was discernible and there was no clear dose-response relationship. There was no QT prolongation noted at any of the doses. Nevertheless, patients with a QT > 450 msec will be excluded from this study, as pre-clinical toxicology showed some tendency to QT prolongation in dog telemetry studies, albeit at high

doses. The ECG abnormalities noted on 24-hour ambulatory monitoring seemed to occur in subjects who already had some similar baseline abnormalities. For this reason, patients with any baseline arrhythmia, including premature ventricular and supraventricular ectopics exceeding 15/min, will be excluded from this study.

No significant laboratory abnormalities of any significance were observed in the FTiM study. However, the haematological and biochemical abnormalities noted in pre-clinical toxicological studies will continue to be monitored in this study also. In addition, patients with a calculated creatinine clearance of <70 ml/min will be excluded as the PK from the FTiM study indicates that the drug is renally eliminated. Excluding these patients would mitigate the risk of high drug exposures related to renal impairment.

For an overall risk benefit/ethical assessment of developing a NE inhibitor in COPD, see the Investigator's Brochure.

3.3 Selection of study population

3.3.1 Study selection record

Investigators must keep a record of patients who were considered for enrolment but were never enrolled e.g. patient screening log. This information is necessary to establish that the patient population was selected without bias.

